## 4.3.2. Safety Endpoints for Year 2 (All Randomized and Treated Patients Proceeding into Year 2)

The safety endpoints listed above in Section 4.3.1 will be evaluated for Year 2 from the first dose of study drug given in Year 2 through week 104E (end of treatment), as well as for the periods of Year 1 and 2 from day 1 through week 104E.

The incidence of JRs at the telephone survey 52 weeks after the last dose of study drug (week 152E) will also be evaluated.

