Note: Any Year 1 patient attending their week 52 visit on or after 26 March 2020 will no longer have the option to enroll into Year 2.

- 1. Completed the treatment period of Year 1
- 2. Did not permanently discontinue study drug during Year 1
- 3. Received no less than 10 of the 13 planned doses of SC study drug during the treatment period of Year 1
- 4. Provide informed consent for Year 2
- 5. Willing to continue to maintain current activity and exercise levels throughout Year 2
- 6. Willing and able to comply with clinic visits and study-related procedures and willing to provide follow-up information related to any JR surgery that occurs within the period of time covered by their intended participation in the study

#### 6.2.4. Exclusion Criteria for Year 2

Women of childbearing potential who are unwilling to continue to practice highly effective contraception during the study, and for at least 20 weeks after the last dose. Highly effective contraceptive measures include stable use of combined (estrogen and progestogen-containing) hormonal contraception (oral, intravaginal, transdermal) or progestogen-only hormonal contraception (oral, injectable, implantable) associated with inhibition of ovulation initiated 2 or more menstrual cycles prior to screening; intrauterine device (IUD); intrauterine hormone-releasing system (IUS); bilateral tubal ligation; vasectomized partner; and or sexual abstinence†‡.

† Sexual abstinence is considered a highly effective method only if defined as refraining from heterosexual intercourse during the entire period of risk associated with the study

treatments. The reliability of sexual abstinence needs to be evaluated in relation to the duration of the clinical trial and the preferred and usual lifestyle of the subject.

‡ Periodic abstinence (calendar, symptothermal, and post-ovulation methods), withdrawal (coitus interruptus), spermicides only, and lactational amenorrhea method (LAM) are not acceptable methods of contraception. Female condom and male condom should not be used together.

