- Continued non-compliance with the protocol, including usage of NSAIDs that are not permitted in the study, after appropriate counseling
- Joint replacement surgery
- AESIs of:
  - Adjudicated arthropathy, as described in Section 9.6.1.1.
  - Sympathetic nervous system dysfunction, as described in Section 9.6.1.2.
- Hepatotoxicity. Study drug should be discontinued if the following are observed:
  - Total bilirubin (TBL) >2x ULN or international normalized ratio (INR) >1.5, and
  - ALT or AST >3x ULN, and
  - No other cause for 1 and 2 is readily apparent

Other causes of ALT, AST, and TBL elevations may include alcoholic hepatitis, autoimmune hepatitis, non-alcoholic hepatitis, heritable diseases (Gilbert's Syndrome), heart failure, and viral hepatitis.

NOTE: Study drug may be withheld in patients who do not meet criteria for permanently discontinuing study drug, until an alternative cause for drug-induced liver injury can be determined. The patient may be re-challenged if an alternative cause for elevated liver function tests is found and the liver function tests return to baseline, but only after discussion with the sponsor.

- Systemic hypersensitivity reaction deemed by the investigator to be related to study drug
- Gastrointestinal bleeding, acute coronary syndrome
- Any other medical need, as determined by the investigator
- Sponsor decision
- Patient decision

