## 10.4.4. Safety Analysis

The summary of safety results will be presented for Year 1, Year 2, and the combined Year 1 and Year 2 treatment periods.

Safety data including TEAEs and treatment emergent AESIs, vital signs, physical exams, laboratory tests, ECGs, and ADA formation will be listed and summarized by treatment group.

Thresholds for potentially clinically significant values (PCSVs) in laboratory parameters and vital signs will be defined by the sponsor and be in effect at the time of final SAP approval.

The time interval to detect any AEs, including AESIs (except JRs identified at the End of Study Phone Calls) is between the first dose of Year 1 study drug injection and the end of Follow-up Period, (either the week 72/Early Termination for those patients not proceeding into Year 2, the week 124E/Early Termination E for those patients proceeding into Year 2, or the Post-Op Joint Replacement Follow-up Visit 2), as well as study drug-related SAEs occurring between the end of Follow-up Period and the End of Study.

For safety variables, the following observation periods are defined:

- The Pretreatment Period is defined as the time from signing the ICF to before the first dose of study drug in Year 1.
- The Year 1 On-Treatment Period is defined as the day from first dose of Year 1 study drug through the day of last Year 1 dose + 4 weeks for those patients not proceeding

into Year 2, or up to the first dose of Year 2 study drug for those patients proceeding into Year 2. Summaries for the Year 1 On-Treatment Period will be based on the SAF – Year 1.

- The Year 1 Post-Treatment Period is defined from the end of the Year 1 On-Treatment Period to the Week 72/Early Termination Visit for those patients not proceeding into Year 2. Summaries for the Year 1 Post-Treatment Period will be based on the SAF Year 1.
- The Year 2 On-Treatment Period is defined as the day from first dose of Year 2 study drug through the day of last Year 2 study drug dose + 4 weeks for those patients proceeding into Year 2. Summaries for the Year 2 Post-Treatment Period will be based on the SAF Year 2.
- The Combined On-Treatment Period is defined as day from first dose of Year 1 study drug through the day of last SC dose + 4 weeks. Summaries for the Combined On-Treatment Period will be based on the SAF Year 1.

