### **1.2.3. Modifications from the Statistical Section in the Final Protocol**

There are no modifications from what is defined and specified in the statistical section of the final protocol.

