**Figure 1: Study Flow Diagram**

Abbreviation: EOS- End of study

Prior to Protocol R475-OA-1611 Amendment 4 Global, patients were randomized 3:3:3:3:1 to receive one of the following treatment regimens:

- Fasinumab 1 mg Q4W - Fasinumab 1 mg SC Q4W and naproxen-matching placebo oral, twice daily
- Fasinumab 3 mg Q4W - Fasinumab 3 mg SC Q4W and naproxen-matching placebo oral, twice daily
- Fasinumab 6 mg Q8W - Fasinumab 6 mg SC Q8W (patients received placebo injections at the study visits where study drug was not administered) and naproxen-matching placebo oral, twice daily

- Naproxen - Fasinumab-matching placebo SC Q4W and naproxen 500 mg oral, twice daily
- Placebo - Fasinumab-matching placebo SC Q4W and naproxen-matching placebo oral, twice daily

A total of 285 patients were enrolled in the fasinumab 3 mg SC Q4W and fasinumab 6 mg SC Q8W groups. However, dosing in these patients was discontinued, as recommended by the independent Data Monitoring Committee (DMC) in April 2018.

Post Protocol R475-OA-1611 Amendment 5 Global approximately 2,560 patients were planned to be randomized 3:3:3:1 to receive:

- Fasinumab 1 mg Q4W - Fasinumab 1 mg SC Q4W and naproxen-matching placebo oral, twice daily
- Fasinumab 1 mg Q8W - Fasinumab 1 mg SC Q8W (patients received placebo injections at the study visits where study drug was not administered) and naproxen-matching placebo oral, twice daily
- Naproxen - Fasinumab-matching placebo SC Q4W and naproxen 500 mg oral, twice daily
- Placebo - Fasinumab-matching placebo SC Q4W and naproxen-matching placebo oral, twice daily

Randomization was stratified according to the affected index joint (hip or knee), the K-L score (2 to 3, or 4) at the screening visit, and geographical region (Europe, North America, and Rest of the World [South Africa]).

Protocol R475-OA-1611 Amendment 6 provided patients the option to continue in the study and receive treatment for an additional year (Year 2). The treatment arm the patients were assigned in Year 2 was determined by the treatment arm they were randomized to in Year 1 according to the following rules:

- Patients randomized to receive Placebo or Naproxen in Year 1 will be assigned to receive Naproxen prn during Year 2
- Patients randomized to received Fasinumab 1 mg Q4W in Year 1 will be assigned to remain on this dose for Year 2
- Patients randomized to received Fasinumab 1 mg Q8W in Year 1 will be assigned to remain on this dose for Year 2

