## 5. STATISTICAL METHODS

For continuous variables, descriptive statistics will include the following: the number of patients reflected in the calculation (n), mean, median, standard deviation, minimum & maximum and 1st & 3rd quartiles (Q1 & Q3).

For categorical or ordinal data, frequencies and percentages will be displayed for each category.

**Period of observation** – Unless otherwise stated, analysis of all safety variables captured at multiple visits will be analyzed by the following observations periods:

- The Pre-Treatment Period is defined as the time from signing the ICF to before the first dose of study drug in Year 1.
- The Year 1 On-Treatment Period is defined as the day from first dose of Year 1 study drug through the day of last Year 1 SC dose + 4 weeks for those patients not proceeding into Year 2, or up to the first dose of Year 2 study drug for those patients proceeding into Year 2. Summaries for the Year 1 On-Treatment Period will be based on the SAF – Year 1.
- The Year 1 Post-Treatment Period is defined from the end of the Year 1 On-Treatment Period to the Week 72/Early Termination Visit for those patients not proceeding into Year 2. Summaries for the Year 1 Post-Treatment Period will be based on the SAF – Year 1.
- The Year 2 On-Treatment Period is defined as the day from first dose of Year 2 study drug through the day of last Year 2 SC dose + 4 weeks for those patients proceeding into Year 2. Summaries for the Year 2 On-Treatment Period will be based on the SAF – Year 2.
- The Year 1 and 2 On-Treatment Period is defined as day from first dose of Year 1 study drug through the day of last SC dose + 4 weeks. Summaries for the Year 1 and 2 On-Treatment Period will be based on both the SAF – Year 1 and SAF-Year 2.
- The Year 2 Post-Treatment Period is defined from the end of the Year 2 On-Treatment Period to the Week 124E/Early Termination E Visit for those patients proceeding into Year 2. Summaries for the Year 2 Post-Treatment Period will be based on the SAF – Year 2.

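### The SAP plans two versions of the 104-week safety summary, one of them conditional on entering Year 2, and does not say which answers objective 5

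*SAP*

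**What the plan says.** Secondary objective 5 (protocol 2.2, SAP 1.2.2) is safety and tolerability against naproxen over as much as 104 weeks. Neither document names an analysis set for it.

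For the period running from the first Year 1 dose to four weeks after the last SC dose, the texts differ:

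- SAP 5: "Summaries for the Year 1 and 2 On-Treatment Period will be based on both the SAF – Year 1 and SAF-Year 2". SAP 5.8.1 then runs the TEAE tables for this period on the sets given in Section 5, and SAP 10.1 lists AA and joint replacements under both sets.
- Protocol 10.4.4: "Summaries for the Combined On-Treatment Period will be based on the SAF Year 1".
- Protocol 4.3.2, whose heading limits it to patients continuing into Year 2, asks for the safety endpoints in Year 2 "as well as for the periods of Year 1 and 2 from day 1 through week 104E".
- SAP 1.2.3: "There are no modifications from what is defined and specified in the statistical section of the final protocol".

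SAF - Year 1 holds every treated FAS patient. SAF - Year 2 holds those given at least one Year 2 dose, grouped by what they received in Year 2 (SAP 3.4). An entry condition for Year 2 is "Did not permanently discontinue study drug during Year 1" (protocol 6.2.3), and the permanent-stop list in protocol 7.3.2.1 includes "Adjudicated arthropathy, as described in Section 9.6.1.1" and joint replacement. On the Year 2 arms, SAP 2.1 says: "Patients randomized to receive Placebo or Naproxen in Year 1 will be assigned to receive Naproxen prn during Year 2".

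In SAP 5.8.7, the Kaplan-Meier curves for time to JR use SAF - Year 1 by Year 1 randomised group. The AA and destructive arthropathy (DA) paragraphs do not say which of the two safety sets applies.

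**The concern.** A table that claims to cover Day 1 onward, but admits only patients who got through Year 1 without a permanent stop, has been selected on the outcome it reports. Eligibility removes the Year 1 stopping events from every arm, and removes more of them from whichever arm had more. If fasinumab has the higher rate, the absolute excess shrinks.

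The same table groups patients by Year 2 treatment, so a Year 1 event that happened on placebo is printed under naproxen.

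Joint harm is the central safety question here: protocol 1.1 records that two higher-dose regimens were dropped in April 2018 after imbalances that included time to total joint replacement. With two 104-week versions and no ranking between them, a report could rest objective 5 on either.

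**Working it through.** No power or alpha figure bears on this. SAP 2.2 sets no power-based sample size for Year 2, and there is no stated figure to reproduce. The check is mainly textual.

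**1. Sets.** Protocol 10.4.4 gives SAF - Year 1. Protocol 4.3.2 gives a view of Year 2 entrants. The SAP uses both and declares no change. The protocol is therefore not of one mind, and the SAP's addition to 10.4.4 is undeclared.

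**2. Selection.** Entry to Year 2 required completing Year 1 treatment, no permanent discontinuation and at least 10 of 13 SC doses (protocol 6.2.3). AA, JR, sympathetic dysfunction, new or worsening carpal tunnel signs, GI bleeding and acute coronary syndrome all force a permanent stop (protocol 7.3.2.1). So a member of SAF - Year 2 should have none of these in Year 1, with one exception. The Week 52E visit is meant to fall on the same day as Week 52 (footnote 17 to protocol Table 2), when bilateral X-rays are taken, so an AA on that film can be adjudicated after entry.

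**3. Grouping.** Planned numbers are naproxen 840 and placebo 280 (protocol 10.2). If placebo patients enter Year 2 at r times the naproxen rate, the former placebo share of the naproxen prn arm is 280r/(280r + 840):

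- r = 1: 280/1120 = 25%
- r = 0.5: 140/980 = 14%
- r = 1.25: 350/1190 = 29%

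**4. Size, by assumption only.** Let p be the annual risk of a stopping event, equal in both years, and f the fraction of event-free patients who enter Year 2. Assume 4% per year on fasinumab and 1% on naproxen.

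- Full 104-week risk, 1 − (1 − p)²: 7.84% and 1.99%. Difference 5.85, about 5.9 points; ratio 3.9.
- Crude incidence on SAF - Year 2, equal to p whatever f is: 4% and 1%. Difference 3.0 points; ratio 4.0.
- Crude incidence on SAF - Year 1, p + (1 − p)fp: at f = 0.3, 5.15% and 1.30%, difference 3.9 points; at f = 0.6, 6.30% and 1.59%, difference 4.7; at f = 1, difference 5.9. This version loses no Year 1 events. It falls short of the full risk only because non-entrants are not followed on treatment in Year 2.
- With 6% and 2% instead: full risks 11.64% and 3.96%, difference 7.7 points, against 4.0 on SAF - Year 2; ratios 2.9 and 3.0.
- Share of all stopping events missing from SAF - Year 2, 1/(1 + (1 − p)f): for p from 1% to 10%, about 50% to 53% at f = 1 and 77% to 79% at f = 0.3.

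**5. Allowing for the Week 52 film.** If a share w of Year 1 AA is confirmed only after entry, and those patients enter at the same rate as event-free patients, the SAF - Year 2 incidence is [pw + (1 − p)p]/[1 − p(1 − w)]. At 4% and 1%:

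- w = 0.25: 0.0484/0.97 = 4.99% and 0.0124/0.9925 = 1.25%, difference 3.7 points
- w = 0.5: 0.0584/0.98 = 5.96% and 0.0149/0.995 = 1.50%, difference 4.5 points

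The shortfall from 5.9 points narrows but does not close.

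**The case against.** A reader might infer that the objective 5 comparison omits most Year 1 joint harm. The documents do not support that. The SAP sentence plans both versions. The SAF - Year 1 version keeps every Year 1 AA and JR and has no former placebo patients in its naproxen column, and nothing ties objective 5 to SAF - Year 2. How much is missing cannot be verified either: arm-level rates and entry numbers are not given, joint events that do not force a stop remain, and some Week 52 AA can remain.

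Nor can it be said that the protocol rules out a summary in Year 2 entrants. Protocol 4.3.2 describes very nearly that population and window. Entry was optional and closed on 26 March 2020, so a companion table in patients who continued is a reasonable description of longer exposure. This stands, and it is why deleting the SAF - Year 2 version is not required.

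Two further points stand. The illustrative loss is in the absolute difference; the ratio hardly moves. And the two defects mostly touch different events: if stopping events are absent by eligibility, few placebo AA or JR are left to be counted as naproxen, so the misgrouping matters mainly for events that do not stop treatment.

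Part of the remedy already exists. Time to JR uses SAF - Year 1, and AA and DA are timed from first dose with censoring. The Cox models for AA and DA take placebo as reference, and only SAF - Year 1 has a placebo group, so that set is probably meant; the text should say so.

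What the objection does not remove is the lack of any ranking or caption, and the undeclared difference from protocol 10.4.4.

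**Conclusion.** The point holds as a matter of reconciliation and labelling with a real bias behind it. The SAF - Year 2 version of the 104-week summary is conditional on having had no permanent Year 1 stop, and its naproxen prn column includes people who spent Year 1 on placebo. The SAF - Year 1 version is sound on both counts for fasinumab versus naproxen. The plan does not say which one answers objective 5.

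The textual part rests on no assumption. The 25% share assumes planned allocation and equal entry. The fall from 5.9 to 3.0 points assumes 4% and 1% annual risks, constant over two years, with no Week 52 AA confirmed after entry. It illustrates the direction and is not an estimate for this trial.

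**What to change.** In SAP 5, state that the Year 1 and 2 On-Treatment Period summarised on SAF - Year 1, by Year 1 arm, is the analysis that answers objective 5.

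In SAP 5.8.7, state that the AA and DA time-to-event analyses use SAF - Year 1 by Year 1 arm, as the JR curves already do.

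If the SAF - Year 2 combined-period tables are kept, caption them as conditional on Year 2 entry and show naproxen-to-naproxen and placebo-to-naproxen patients in separate columns.

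Declare the added set in SAP 1.2.3, and reconcile protocol 10.4.4 with protocol 4.3.2.

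The cost is SAP wording, one extra column and some captions. No new data are needed.

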### 5.1. Demographics and Baseline Characteristics

Demographic and baseline characteristics described in Section 4.1 will be descriptively summarized by treatment group and overall for the study based on the mFAS, FAS, SAF – Year 1 and SAF – Year 2.

### 5.2. Medical History

All reported patient's medical history and surgical history will be presented showing patient counts (percentages) by primary SOC and PT by treatment group and overall for the study based on the SAF – Year 1. The tables will be sorted by decreasing frequency of primary SOC in the

overall group. Within each primary SOC, PTs will be sorted by decreasing frequency in the overall group. The same summaries will be also be supplied based on the SAF – Year 2.

### **5.3. Prior/Concomitant Medications**

Summaries will present patient counts (and percentages) for all medications, dictionary coded by WHO, by decreasing frequency of the overall group incidence (or fasinumab 1mg Q4W group incidence in tables where the overall is not presented) of ATC followed by ATC level 2, ATC level 4 and preferred term. In case of equal frequency across anatomic or therapeutic categories, alphabetical order will be used. Patients will be counted once in each ATC category (anatomic or therapeutic) linked to the medication but may be counted several times for the same medication.

The following will be summarized:

- All prior medications will be summarized by treatment group and overall, based on the SAF – Year 1 and the SAF – Year 2 separately.
- All concomitant medications taken during the Year 1 On-Treatment Period will be summarized by treatment group based on the SAF – Year 1. Similarly, all concomitant medications taken during the Year 2 On-Treatment Period will be summarized by treatment group based on the SAF – Year 2.
- All Post-treatment medications taken during the Year 1 Post-Treatment period will be summarized by treatment group based on the subset of patients in the SAF – Year 1 who do not continue into Year 2. For patients who continue into Year 2, all concomitant medications taken during the Year 2 Post-Treatment period will be summarized by treatment group based on the SAF – Year 2.

### **5.4. Prohibited Medications**

Summaries of prohibited medications will present patient counts (and percentages) for all prohibited medications, dictionary coded by WHO, by decreasing frequency of the overall group incidence (or fasinumab 1mg Q4W group incidence in tables where the overall is not presented) of ATC followed by ATC level 2, ATC level 4 and preferred term. In case of equal frequency across anatomic or therapeutic categories, alphabetical order will be used. Patients will be counted once in each ATC category (anatomic or therapeutic) linked to the medication but may be counted several times for the same medication. The following will be provided:

- All prohibited medications taken during the Pre-Treatment Period will be summarized by treatment group and overall, based on the SAF – Year 1 and SAF – Year 2 separately.
- All prohibited medications taken during the Year 1 Treatment and Follow-up Periods will be summarized by treatment group based on the SAF – Year 1. An analogous analysis will be performed for Year 2 Treatment and Follow-up Periods based on the SAF – Year 2.
- All prohibited NSAID medications taken during the Year 1 Treatment and Follow-up Periods will be summarized by treatment group based on the SAF – Year 1. An analogous analysis will be performed for Year 2 Treatment and Follow-up Periods based on the SAF – Year 2.

- The total number of days using prohibited NSAIDs during the Year 1 Treatment and Follow-up Periods (before AA for patients with AA) will be summarized by treatment group based on the SAF – Year 1. An analogous analysis will be performed for the Year 2 Treatment and Follow-up Periods based on the SAF – Year 2.
- The number of days from the last dose of study drug in Year 1 to the first NSAID dose will be summarized in the subset of patients in the SAF – Year 1 who do not continue into Year 2. Similarly, the number of days from the last dose of study drug in Year 2 to the first NSAID dose will be summarized based on the SAF – Year 2.

## 5.5. Subject Disposition

In addition to the summaries in the following subsections, the following will be provided:

- The total number of screened patients: defined as having signed the ICF
- The total number of randomized patients (defined in the protocol as having received a randomization number).
- The total number of patients in each analysis set.
- A listing of patients treated but not randomized, patients randomized but not treated and patients randomized but not treated as randomized.
- A listing of disposition for all patients.
- A listings of screening failures and reasons for screen failing.
- A listing of patients prematurely discontinued from treatment, along with reasons for discontinuation.
- A listing of patients who withdrew from the study, along with reasons for study withdrawal.

